#### **REVISION CHRONOLOGY:**

Date	Version	Change(s) since last version
15-JUN-2020	Original	N/A
27-JUL-2020	Amendment 01	
 
Addition of benefit/risk assessments
 
Addition of detailed description of each study period (screening period, observation period and follow-up period)
 
Change of time period for collecting AE
 
Change of Table for Schedule of activity
 
Removal of the opportunity of review by the identified investigator for the study reports
 
Change of a duration for retaining records and documents
 

Copyright 2020 the GlaxoSmithKline group of companies. All rights reserved. Unauthorized copying or use of this information is prohibited.

# **ABBREVIATIONS**

ADEs	Adverse device effects
ADRs	Adverse drug reactions
AEs	Adverse events
AESI	AEs of special interests
CCI	The of openin merces
ASE	All Subjects Enrolled
CCI	7 th Cubjecto Efficient
CIOMS	Council for International Organizations of Medical Sciences
CROs	Contract Research Organisations
CCI	- V
DBF	Database freeze
DBR	Database release
eCRF	Electronic case report form
CCI	
EGPA	Eosinophilic granulomatosis with polyangiitis
ENT	Ear, nose, and throat
CCI	
CCI	
GSK	GlaxoSmithKline
HCP	Healthcare Professional
HIPAA	Health Insurance Portability and Accountability Act
ICF	Informed consent form
ICH	International Council for Harmonisation
ICMJE	International Committee of Medical Journal Editors
IEC	Independent Ethics Committee
IHD	Individual human data
IL-5	Interleukin-5
MedDRA	Medical Dictionary for Regulatory Activities
MPO	Myeloperoxidase
MT	Malignant tumour
OCS	Oral corticosteroid
PDMP	Protocol Deviation Management Plan
PML	Progressive multifocal leukoencephalopathy
PMS	Post marketing surveillance
CCI	
RAP	Reporting and Analysis Plan
RCT	Randomized controlled trial
RMP	Risk management plan
SADEs	Serious adverse device effects
SAEs	Serious adverse events
SoA	Schedule of Activities
SRM	Study reference manual
sPVP	Study-specific pharmacovigilance plan
TP	Treated Population

# **Trademark Information**

Trademarks of the GlaxoSmithKline		
group of companies		
Nucala		

Trademarks not owned by the GlaxoSmithKline group of companies

#### 1. BACKGROUND AND RATIONALE

Eosinophilic granulomatosis with polyangiitis (EGPA), formerly known as the Churg-Strauss syndrome, is a systemic necrotizing vasculitis that affects small and medium sized blood vessels [Groh, 2005]. It is characterized by asthma, sinusitis, pulmonary infiltrates, neuropathy, and eosinophilic vasculitis of one or more organs [Jennette, 2013; Churg, 1951; Cottin, 2016; Guillevin, 1999].

Eosinophils contribute to the pathophysiology of EGPA by tissue and vascular infiltration and inflammation through different kinds of mediators [Akuthota, 2012; Khoury, 2014]. The cytokine interleukin-5 (IL-5) plays a crucial role in regulating the life cycle of eosinophils [Lopez, 1988; Rothenberg, 2006; Clutterbuck, 1989], and is found in very high levels in patients with EGPA [Hellmich, 2005]. Therefore, neutralization of IL-5 with mepolizumab, a humanized anti-IL5 monoclonal antibody, is a therapeutic option for EGPA [GlaxoSmithKline Document Number 2012N142276\_03].

In Japan, 3401 patients with EGPA were certified as recipients of specific disease treatment [Japan Intractable Diseases Information Center, 2019]. According to a cross-sectional nationwide survey conducted by Sada et al., the prevalence of EGPA in Japan was estimated at 17.8 per 1,000,000 adults [Sada, 2014], which is similar to the prevalence reported in western countries (10.7-13 per 1,000,000 individuals) [Mahr, 2004; Martin, 1999]. In Japan, EGPA is one of the designated intractable diseases for promoting research to clarify the pathogenesis and to develop pharmaceutical products and medical devices, as well as to financially support patients with these diseases [Japan Intractable Diseases Information Centre, 2019].

Nucala (mepolizumab 300 mg, subcutaneous administration) was approved in Japan in 2018 for the treatment of EGPA in adult patients who inadequately respond to existing therapies [Nucala, 2020]. As the number of Japanese patients in clinical trials was limited, a Post marketing surveillance (PMS) study, special drug use investigation after its market launch, has been conducted in all patients administered Nucala for the treatment of EGPA in order to collect and assess information on the safety and effectiveness of the long-term use of Nucala in daily clinical practice in patients with EGPA [GlaxoSmithKline PMS protocol No. 208505]. However, the observation period of this PMS study is limited to up to 96 weeks (approximately 2 years) per patients from the start of Nucala administration. There have been no reports to date assessing the long-term safety and effectiveness of Nucala when used continuously beyond 96 weeks (approximately 2 years). There exists no-evidence not only in Japan, but also worldwide.

This study aims to assess the long-term safety and effectiveness of Nucala in the real-world setting in patients with EGPA who have already used Nucala for 96 weeks (approximately 2 years) after its market launch in Japan.

#### 1.1. Benefit/Risk Assessment

#### 1.1.1. Risk Assessment

This study does not involve the administration of any study treatment intervention to participants nor invasive study procedures. No potential risks beyond the routine clinical practice are considered in relate to participating in this study.

#### 1.1.2. Benefit Assessment

By participating in this study, participants will be contributing to the understanding of long-term safety and efficacy of Nucala in a Japanese population, which may help provide a treatment option in the future.

[figure not shown]
#### 1.1.3. Overall Benefit: Risk Conclusion

[figure not shown]
In the overall benefit-risk assessment, any risks that will affect the conduct of this study are not identified.

#### 2. OBJECTIVES/ENDPOINTS

The objective of this study is to collect and assess information on the long-term (2 to 4 years) safety and effectiveness of Nucala (mepolizumab 300 mg, subcutaneous administration) in patients with EGPA, who have already used Nucala for 96 weeks (approximately 2 years), in real-world settings in Japan.

Objectives	Endpoints
Primary	
To investigate the long-term safety of Nucala in adult patients with EGPA	• Frequency of Adverse events (AEs)/ serious adverse events (SAEs)
	• Frequency of AEs related to Nucala (adverse drug reactions, ADRs)
	• Frequency of AEs of special interests (AESI)
Secondary	
To investigate the long-term effectiveness of Nucala in adult patients with EGPA	• Proportion of participants with clinical symptoms as assessed by 9 organ-systems (i.e. systemic, skin, mucous membranes/eyes, ears/nose/throat, chest, cardiovascular, abdominal, renal, nervous system)
	• Proportion of participants with EGPA relapse a
	
 
Annualized rate (event/year) of hospitalization for EGPA-related events
 

	Annualized rate (event/year) of emergency

a. EGPA relapse is defined as any of the following with worsening EGPA. 1) Increased dose of OCS. 2) Initiation/increased dose of immuno-suppressive agents. 3) EGPA treatment with hospitalization (Section 4.6).

### 3. RESEARCH METHODOLOGY

# 3.1. Study Design

This is a single-arm, multi-center, prospective, non-interventional, observational study to assess the long-term (2 to 4 years) real-world safety and effectiveness of Nucala in adult patients with EGPA who have already received Nucala treatment for 96 weeks (approximately 2 years) after its market launch in Japan and who completed the Nucala

[figure not shown]
b. EGPA recurrence is judged by investigator based on the following definitions (only in participants who have been withdrawn from/terminated the Nucala treatment and entered the follow-up period due to symptom improvement per clinical judgement):1) Initiation/increased dose of OCS, 2) Initiation/increased dose of immuno-suppressive agents, 3) Hospitalization in association with the EGPA treatment (Section 3.4).

PMS study (special drug use investigation; Protocol No. 208505, NCT03557060). To reflect the real-world setting, inclusion and exclusion criteria as well as concomitant treatment criteria are limited to the minimum required. Approximately 120 participants will be enrolled in the study.

The primary objective is to investigate the long-term safety of Nucala, with special attention to AEs, AESI, and SAEs, in adult patients with EGPA in Japan. The effectiveness of Nucala will also be investigated as secondary and exploratory objectives. Endpoints for effectiveness are included in reference to endpoints in the PMS study.

The study schema is provided in Figure 1. The data in the routine clinical practice will be collected in the study.

Figure 1 Study Schema

This study is an observational study that does not involve the administration of study treatment intervention. According to the Japanese prescribing information for Nucala, 300 mg mepolizumab is injected subcutaneously every 4 weeks in adult patients with EGPA, who inadequately respond to other existing therapies. Participants receive marketed products of Nucala in any of the approved formulations; lyophilized products and/or liquid products (prefilled syringe/auto-injector pen).

This study is composed of three periods: screening period, observation period and follow-up period.

#### **Screening period**

During the screening period (0-4 weeks), all participants are assessed to determine whether they meet the eligibility criteria. Retrospective data are collected for reference regarding the clinical symptoms/findings and laboratory parameters before the first dose of Nucala (at least 96 weeks [approximately 2 years] before). These retrospective data should be from physician source/medication record. By using the retrospective data,

information could be provided about the change from pre-Nucala exposure to the end of this study, of which a period would be approximately 4 years.

Any participant who completes assessments during the screening period but does not continue in the study beyond Baseline or is subsequently found to be ineligible for the study prior to Baseline, is classified as Screen Failure. Information collected for the participant classified as Screen Failure is detailed in the guideline for eCRF entry. Rescreening is permitted once only.

#### **Observation period**

During the observation period, which is scheduled for 96 weeks (approximately 2 years) at maximum, safety and effectiveness data are obtained at approximately 12-week intervals. The intervals may be shorter/longer or may be irregular depending on the usual pattern of healthcare visits.

Any data collected during the observation period are entered into eCRF. The assessments in the routine clinical practice during the observation period are shown in Section 9.1 (Appendix 1).

#### Follow-up period

The follow-up period is only applicable to participants who have discontinued the treatment of Nucala due to any reason. The assessments in the routine clinical practice during the follow-up period are shown in Section 9.1 (Appendix 1).

In case EGPA symptoms are deteriorated in a participant who previously discontinued the treatment of Nucala due to improvement of EGPA symptoms, the participant can receive the re-treatment of Nucala during the follow-up period. The participant who received the re-treatment of Nucala continues the assessments in the follow-up period.

#### 3.2. Data Source / Data Collection

#### CRF data

For this study, participant data will be entered into GlaxoSmithKline (GSK)-defined Electronic case report forms (eCRFs), transmitted electronically to GSK, and combined with data provided from other sources in a validated data system. Personal information such as "participant name", "participant initial" and "full date of birth" will not be collected in eCRF, and each participant will be managed with Subject ID in eCRF and clinical database for anonymization.

Management of clinical data will be performed in accordance with applicable GSK standards and data cleaning procedures to ensure the integrity of the data, e.g., removing errors and inconsistencies in the data.

eCRFs (including queries and audit trails) will be retained by GSK and copies will be provided to the investigator to be maintained. Participant initials will not be collected and transmitted to GSK according to a GSK policy.

## 3.3. Eligibility Criteria

#### 3.3.1. Inclusion Criteria

Participants are eligible to be included in the study only if **all** of the following criteria apply:

- 1. Adult patients with EGPA of ≥20 years of age inclusive, at the time of signing the informed consent.
- 2. Participants must have a current clinical diagnosis of EGPA by physician.
- 3. Participants have continuously used Nucala for at least 96 weeks for the treatment of EGPA as mentioned in the current label in Japan.
  - Participants thus were registered and completed the Nucala PMS study (special drug use investigation; Protocol No. 208505, NCT03557060) prior to be enrolled in this study.
- 4. Physician's decision to continue treatment with Nucala for the treatment of EGPA as mentioned in the current label in Japan.
- 5. Prior to commencing any study related activities, participants must be able and willing to provide written informed consent.

#### 3.3.2. Exclusion Criteria

A participant will not be eligible for inclusion in this study if any of the following criteria apply:

- 1. Participants who have previously discontinued Nucala treatment for EGPA for more than 12 weeks.
- 2. Participating in another clinical trial within the past 12 months, in which the participant has been exposed to an investigational or non-investigational pharmaceutical product.
- 3. Participants with any reasons that in physician's opinion would place the patients at risk
- 4. Participants who are pregnant or breastfeeding.

#### 3.3.3. Withdrawal from Study

- A participant may withdraw from the study and stop reporting data at any time at his/her own or physician's request, or if they are lost to follow-up.
- To determine the safety and effectiveness of Nucala administration in participants who discontinued the treatment, a follow-up investigation (up to planned Week 96 of observation period) should be conducted wherever possible.
- If the participants enroll in another study involving investigational study treatment intervention while enrolled in this study, they will be withdrawn from the present study.

#### 3.4. Variables

The investigator will collect information about the following variables wherever possible and record it on the eCRF. The timing of collecting information is listed in Section 9.1 (Appendix 1) (SoA).

- Demography: Age, sex, body weight, height, EGPA severity classification\*, and medical history/comorbidity
- \*Defined by Japan Intractable Diseases Information Center (Japan Intractable Diseases Research Foundation)
- Administration status of Nucala for EGPA, including product formulation information
- Concomitant medications and therapies
- Adverse events, SAEs, and AESI \*
- \*AESI: hypersensitivity (including anaphylaxis), infections and malignant tumors, defined as safety specifications in the Japanese RMP
- Clinical symptoms (only disease activities relevant to EGPA in systemic vasculitis assessed) of the following 9 organ systems [Sada, 2014]:
  - 1) Systemic
  - 2) Skin
  - 3) Mucous membranes/eyes
  - 4) Ear, nose and throat (ENT)
  - 5) Chest
  - 6) Cardiovascular

- 7) Abdominal
- 8) Renal
- 9) Nervous
- Hospitalization for EGPA-related events
- Emergency room/unscheduled visit for EGPA-related events
- Asthma exacerbation as defined below:
  - 1) Exacerbation of bronchial asthma which requires hospitalization
  - 2) Exacerbation of bronchial asthma which requires emergency room visit
  - 3) Exacerbation of bronchial asthma which requires the use of systemic steroids\*

When a participant requires continuous administration of steroids systemically, in concrete terms, orally, intravenously or intramuscularly, for  $\geq 3$  days. However, as for intramuscular injection, it must also include a continuous administration of dexamethasone sodium phosphate or betamethasone sodium phosphate for  $\geq 3$  days, or one or more doses of triamcinolone acetonide.

When a participant receiving the maintenance therapy with systemic steroids requires doubling the maintenance dose for  $\geq 3$  days for exacerbation of bronchial asthma.

Exacerbations that occurred <7 days from the last exacerbation were treated as a continuation of the same exacerbation.

- Clinical laboratory parameters:
- Lung function: (with reason for examination of pulmonary function)

Pre- and post-bronchodilator values will be collected as respective separate categories. If it is not known whether the reading is pre- or post-bronchodilator, this will be collected as unknown.

- CCI
- EGPA recurrence is judged by investigator based on the following definitions (only in participants who have been withdrawn from/terminated the Nucala treatment and entered the follow-up period due to symptom improvement per clinical judgement):
  - 1) Initiation/increased dose of OCS

\*The standard definitions for the use of systemic steroids are as follows:

- 2) Initiation/increased dose of immuno-suppressive agents
- 3) Hospitalization in association with the EGPA treatment

Note that EGPA relapse is defined in Section 4.6.

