#### To investigate the maintenance of response after cessation of Nucala treatment

• Time to EGPA recurrence up to Week 96 in participants who discontinued/withdrew from Nucala treatment due to symptom improvement.

Summaries and graphs of the Kaplan-Meier estimates of the proportion of participants with an EGPA recurrence over time will be produced. (Definition of EGPA recurrence: See Section 3.4).

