#### 9. APPENDIX

# 9.1. APPENDIX 1: SCHEDULE OF ACTIVITIES (SOA)

Procedure	Screening		Observation period			Follow-up 
Time period for which data should be collected at	Up to 4 we	eks before Week 0 	Week 0	Week 12 to 96;	Early	Up to 96 weeks
usual EGPA healthcare visits,	(Screening  )	(Retrospective data 	Baseline	no more frequently than	withdrawal	after Week 0
if this is possible		collection)		every 12 weeks (±4weeks)		
Informed consent	X 					
Inclusion and exclusion criteria	Χ					
Demography	X					
Administration status of Nucala for EGPA	X		Χ	Χ	Χ	X 5
Concomitant medication	X	X6	Χ	Χ	Χ	X
Concomitant therapies	X	X 	Χ	X	Χ	X
Adverse events	X		+			→
Clinical symptoms		Χ	Χ	Χ	Χ	X
Hospitalization for EGPA-related events		X8	Χ	X	Χ	X
ER/Unscheduled visit for EGPA-related events		X8	Χ	Χ	Х	X
Asthma exacerbation		X8	Χ	Χ	Х	X
Clinical laboratory parameters  , if performed		Х	Χ	Χ	Χ	X
Lung function, if performed		Х	Χ	X	Χ	X
Ejection fraction, if performed		Х	Χ	Χ	Χ	X
Pregnancy reporting			•		-	
EGPA recurrence						X

- 1. The follow-up period is only applicable for participant who discontinued the treatment. If drug-related adverse events occurred, contact the sponsor.
- 2. Screening and Week 0 can occur on the same day.
- 3. Retrospective data within 12 weeks (otherwise specified) before the first dose of Nucala for EGPA.
- 4. Informed consent must be obtained prior to start of any study's procedure.
- 5. Only for in case of receiving the re-treatment of Nucala.
- 6. Only for other biological products, Nucala for asthma, corticosteroid, immunosuppressants, and immunoglobulin.
- 7. Only for EGPA therapies.
- 8. Number of events within 48 weeks before the first dose of Nucala for EGPA.
- 9. Haematological parameters tested are:

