1.1. Objectives and Endpoints

Objectives	Endpoints
Primary	
• To investigate the long-term safety of Nucala in adult patients with EGPA	• Frequency of Adverse events (AEs)/ serious adverse events (SAEs)
	• Frequency of AEs related to Nucala (adverse drug reactions, ADRs)
	• Frequency of AEs of special interests (AESI)
Secondary	
• To investigate the long-term effectiveness of Nucala in adult patients with EGPA	• Proportion of participants with clinical symptoms as assessed by 9 organ-systems (i.e. systemic, skin, mucous membranes/eyes, ears/nose/throat, chest, cardiovascular, abdominal, renal, nervous system)
	• Proportion of participants with EGPA relapse ^a
	• Annualized rate (event/year) of hospitalization for EGPA-related events
	• Annualized rate (event/year) of emergency room/unscheduled visit for EGPA-related events
	• Average daily dose (prednisolone- equivalent) of oral corticosteroid (OCS) over 96 weeks
	• Proportion of participants in the dosing categories [*] relative to average

Objectives	Endpoints
	daily OCS (prednisolone-equivalent) over 96 weeks * 0 mg/day 0 mg/day < < 4 0
	$mg/day, 4.0 mg/day < \leq 7.5 mg/day,$ 7.5 mg/day <
Exploratory	
CCI	

a. EGPA relapse is defined as any of the following with worsening EGPA. 1) Increased dose of OCS. 2) Initiation/increased dose of immuno-suppressive agents. 3) EGPA treatment with hospitalization.
b. EGPA recurrence is judged by investigator based on the following definitions (only in participants who have been withdrawn from/terminated the Nucala treatment and entered the follow-up period due to symptom improvement per clinical judgement):1) Initiation/increased dose of OCS, 2) Initiation/increased dose of immuno-suppressive agents, 3) Hospitalization in association with the EGPA treatment.

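### EGPA recurrence after stopping Nucala does not count restarting Nucala, so a deterioration managed by restart alone is not an event in the maintenance-of-response analysis

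*Protocol*

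**What the plan says.** Protocol 3.4 defines the variable: "EGPA recurrence is judged by investigator based on the following definitions". It applies only to participants who stopped Nucala and "entered the follow-up period due to symptom improvement per clinical judgement". SAP 1.1, footnote b, gives the same closed list: "1) Initiation/increased dose of OCS, 2) Initiation/increased dose of immuno-suppressive agents, 3) Hospitalization in association with the EGPA treatment".

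Protocol 3.1 (Follow-up period) covers the case where symptoms deteriorate in someone who stopped because of improvement: "the participant can receive the re-treatment of Nucala during the follow-up period". That participant then stays in follow-up.

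Protocol 4.6 uses the variable for the objective on maintenance of response after cessation. The endpoint is "Time to EGPA recurrence up to Week 96 in participants who discontinued/withdrew from Nucala treatment due to symptom improvement", shown by Kaplan-Meier.

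The schedule of activities (Protocol 9.1) collects Nucala administration status in follow-up, with footnote 5: "Only for in case of receiving the re-treatment of Nucala".

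No visible text says whether a restart is an event, a censoring point or neither. SAP 4.4, where exploratory endpoints are analysed, is redacted.

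**The concern.** The endpoint asks how long response lasts once Nucala is withdrawn. It recognises loss of response through treatment escalation or admission. The one escalation that the protocol names for this group, going back on Nucala, is not on the list. A participant who deteriorates and only restarts Nucala has lost the response in the sense of the objective but has no recurrence by the definition.

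At stake is the only endpoint that Protocol 4.6 lists under the cessation objective. A reader will take its recurrence-free curve as evidence on how safely Nucala can be stopped after improvement. The subset is probably small, so a few unclassified restarts could change that reading.

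**Working it through.** **Passages side by side**

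| Item | Recurrence endpoint | Re-treatment provision |
|---|---|---|
| Who | Stopped Nucala because of improvement (Protocol 3.4) | Stopped Nucala because of improvement (Protocol 3.1) |
| Trigger | One of three: OCS, immunosuppressant, hospitalization | Deteriorated EGPA symptoms |
| Afterwards | Time to event, up to Week 96 (Protocol 4.6) | Remains in follow-up (Protocol 3.1) |

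The populations coincide, and the re-treatment trigger is itself a loss of response. Restart alone satisfies none of the three criteria.

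**The plan's own figures.** The documents give no number for this endpoint: not how many will stop for improvement, how many will deteriorate, or how many will restart. The only sample-size figure (Protocol 3.5) concerns adverse events: 107/(1 − 0.10) = 118.9, so 119, stated as approximately 120. It reproduces but has no bearing here.

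**Effect per participant.** If nobody is censored earlier and the restart is ignored, each restart-only participant moves the recurrence-free proportion by 1/n. For an assumed n of 5 to 30, that is 1/5 = 20 to 1/30 = 3.3 percentage points.

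**Three ways of not counting a restart.** Let p be the true proportion deteriorating by the end of follow-up and f the share of those managed by restart alone. Time to deterioration is taken as exponential. All these values are assumptions.

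- Benchmark, restart counted as an event: recurrence-free = 1 − p.
- (A) Restart ignored, never an event: 1 − p(1 − f).
- (B) Censored at restart: (1 − p)^(1 − f).
- (C) Kept at risk on drug, with the event hazard after restart assumed to be 20% of the earlier hazard: by simulation.

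| p | f | Benchmark | A | B | C |
|---|---|---|---|---|---|
| 30% | 0 | 70.0% | 70.0% | 70.0% | 70.0% |
| 30% | 25% | 70.0% | 77.5% | 76.5% | 77.2% |
| 30% | 50% | 70.0% | 85.0% | 83.7% | 84.5% |
| 30% | 75% | 70.0% | 92.5% | 91.5% | 91.7% |
| 50% | 0 | 50.0% | 50.0% | 50.0% | 50.0% |
| 50% | 25% | 50.0% | 62.5% | 59.5% | 61.6% |
| 50% | 50% | 50.0% | 75.0% | 70.7% | 73.2% |
| 50% | 75% | 50.0% | 87.5% | 84.1% | 84.8% |

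Worked line: p = 30%, f = 50%. A = 1 − 0.30 × 0.50 = 0.850. B = 0.70^0.50 = 0.837.

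All three options lie above the benchmark whenever f > 0. The rise runs from 76.5 − 70.0 = 6.5 to 87.5 − 50.0 = 37.5 points. Censoring does not remove it: Kaplan-Meier assumes that those censored have the same future risk as those still followed, and here they are censored because they have just deteriorated. Under C, a later OCS increase is counted but dated after the loss of response.

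**The opposite effect.** Relapse (Protocol 4.6) requires worsening EGPA; the recurrence criteria as printed do not. An OCS increase for another reason might be counted. With r restart-only participants missed and u unrelated escalations counted, and no censoring, the net shift in the recurrence-free proportion is (r − u)/n. Neither r nor u is known.

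**The case against.** **Redaction.** SAP 4.4 could treat restart as an event, a competing event or a sensitivity analysis. This stands as a limit on what can be said about the analysis. It does not touch the event definition, which is visible and the same in both documents, and SAP 4.8 declares no change from the protocol's analyses.

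**Investigator judgement.** An investigator might call a restart a recurrence. But the judgement is tied to a list of three, and discretion outside the list could differ between sites.

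**Deterioration is visible elsewhere.** Symptoms, including worsening, are tabulated for follow-up (SAP 4.3.1.2.1), and exposure is summarised for follow-up and listed (SAP 4.5.1). This is partly right, but the follow-up tables include everyone who stopped for any reason and do not alter the time-to-recurrence curve.

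**Low consequence.** The study is descriptive, time to recurrence is not among the secondary endpoints in SAP 4.3.1.1, and Protocol 5 already warns that effectiveness data will be thin. This stands and limits the severity.

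**Mixed follow-up tables.** A reader might also object that follow-up tables pool off-drug with back-on-drug visits. The protocol says openly that re-treated participants remain in follow-up and does not present the period as drug-free. Splitting those tables is a reporting preference.

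**Conclusion.** The definition is incomplete for its own objective: a deterioration managed by restarting Nucala alone is not a recurrence event, in the very population for which re-treatment is provided. Relative to counting the restart, each of the three alternatives raises the recurrence-free proportion.

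A reader might infer that maintenance of response is overstated. The documents do not support that flat statement. The effect is zero if every restart comes with or after another criterion. Unrelated OCS increases might pull the other way, so the net direction is not fixed. A rule in the redacted section also cannot be excluded.

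The table and the 3.3 to 20 points per participant rest on assumed values and show the mechanism; they are not estimates for this study. The primary safety analysis is unaffected. Severity is low to moderate.

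**What to change.** In the time-to-recurrence analysis, add a derived endpoint, recurrence or Nucala re-initiation. The event is the earlier of the investigator-judged recurrence and the first Nucala re-treatment given for deteriorated EGPA symptoms, dated at that dose. Show the present three-criterion curve beside it, and report how many participants were re-treated. If SAP 4.4 already contains such a rule, a reference to it at SAP 1.1, footnote b, is enough.

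Deriving the endpoint leaves the investigator-recorded variable as it is. The re-treatment record is already collected under footnote 5 of the schedule of activities.

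The cost is one extra derivation, confirmation of the reason for each restart, and possibly a less favourable recurrence-free proportion. The change concerns the counting of events only and leaves the clinical re-treatment provision untouched.
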